6.4 Additional Analyses

Additional analyses include those pertaining to the Opioid-overdose Reduction Continuum of Care Approach (ORCCA). The ORCCA consists of three menus of EBPs that were implemented in Wave 1 communities. Within each menu, EBPs were implemented in different combinations of strategies

(e.g., active opioid overdose education and naloxone distribution at high-risk venues), sectors (e.g., healthcare), and venues (e.g., healthcare-emergency department). Each strategy-sector-venue combination is referred to as a triad. A triad is the primary identifier for a strategy that is planned and then implemented within a community. For each triad that is selected by a community, respondents were asked specific questions relating to:

- intent to reach special populations;
- development of an implementation plan for the strategy;
- initiation of the implementation plan;
- the number of partner organizations/practices that are implementing the strategy; and
- a brief description of the strategy.

To summarize this information across Wave 1 communities, Table 6 (see Section 6.7) may provide frequencies and percentages of strategy and sector for each of Menu 1: Overdose Education and Naloxone Distribution (OEND), Menu 2: Medication for Opioid Use Disorder (MOUD), and Menu 3: Safer Prescribing. Summaries will be presented by RS (KY, MA, NY, OH), by geographic location (urban, rural), and overall. The table will only include summary statistics on menus that are relevant to the manuscript. For this manuscript, all menus will be summarized.

Depending on the scope of the manuscript, frequencies and percentages for specific strategy-sector-venue strategies may also be included. Inclusion will be informed by: 1) the ORCCA Overview, which maps outcome measures to ORCCA menus and strategies; and 2) the sector and venue definitions provided in Appendix D of the ORCCAT SOP, which were vetted by the Common Implementation Metrics workgroup.

After Version 3.0 of the SAP was implemented and results were disseminated, one additional analysis was conducted to estimate the effect of the CTH intervention of the relative rate of opioid overdose deaths between the evaluation and baseline periods. In this case, a repeated measures marginal model (similar to those described in Section 6.2.6 for age, sex, and race/ethnicity subgroup analyses) was fit to the number of opioid overdose deaths during the baseline and evaluation periods. Fixed effects included wave, research site, urban/rural status, time period (baseline or evaluation period), and a two-way interaction between wave and time period as well as an offset term given by the natural log of the community population size during the most recent year from available data. A residual covariance structure was specified to account for correlation among outcomes measured at baseline and evaluation periods within the same community. In this case, the effect of the CTH intervention was estimated using the ratio (and 95% CI and p-value) between the following two estimates:

- The adjusted relative rate (and 95% CI) of opioid overdose deaths between the evaluation and baseline periods in Wave 1 communities.
- The adjusted relative rate (and 95% CI) of opioid overdose deaths between the evaluation and baseline periods in Wave 2 communities.

After Version 3.0 of the SAP was implemented and results were disseminated, the study team requested an estimate of the number of “deaths averted” from implementing the CTH intervention in Wave 1. Two methods were used to estimate the number of deaths averted: (1) a crude method that does not account for overdispersion or covariates, and (2) a model-based average marginal effects method (Greene, 2000) using the estimated parameters from the negative binomial used for the primary analysis.

1. Crude method: apply the observed rate in Wave 2 communities (number of OOD deaths/population, the Wave 1 counterfactual) to the Wave 1 population. We then subtract the actual observed deaths from the Wave 1 counterfactual to get the estimated deaths averted.
2. Negative binomial based method: use the parameter estimates from the negative binomial model used for the primary analysis to estimate Wave 1 predicted deaths using Wave 2 parameters (Wave 1 counterfactual). We then used the Wave 1 parameters to estimate Wave 1 predicted deaths (Wave 1 as Wave 1). We subtracted the Wave 1 as Wave 1 from the Wave 1 counterfactual to get the estimated deaths averted.

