2.1 Background and Rationale

The U.S. opioid OD epidemic has been declared a national emergency.^{2,3} Currently, a menu of EBPs for OUD prevention and treatment spanning the OUD continuum of care exists. Unfortunately, uptake and implementation of these EBPs remains low in numerous community settings including addiction treatment, harm reduction general medical care, social support services, schools, and the justice system. This failure is in part due to a lack of evidence-based approaches for assisting communities in the development and deployment of a data-driven, custom-designed response strategy to deliver comprehensive integrated EBPs. Many of the study counties/communities lack integrated service systems for OUD.

Using a data-driven, multi-pronged, community-based approach is necessary to change the course of the epidemic. The HEALing Communities Study (HCS) is a 5-year, multi-site, parallel arm, cluster randomized wait-list controlled trial to test the immediate impact of implementing an integrated set of EBPs from the CTH framework delivered across healthcare, behavioral health, justice, and other community-based settings in highly affected communities. The HCS is designed to detect a 40% reduction in the rate of opioid OD deaths between randomized arms after two years of intervention, with the primary comparison planned for the evaluation period, defined as the 12-month period from July 1, 2021 to June 30, 2022.

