5.5 Baseline Community Characteristics

Baseline counts and rates of opioid OD deaths in HCS communities, and other outcome measures needed for the statistical analysis, will be collected based on the 12 months from January 2019 to December 2019 immediately preceding the study initiation and implementation of CTH intervention in Wave 1 communities. Additionally, baseline counts and rates will be used for dashboard visualization measures, where available. Baseline data may be used in additional RS-specific analyses, including geospatial analyses using address information (e.g., from death certificate data, including address of death and address of residence) where permitted by RS's state-specific data use agreements.

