6.2.1 Statistical Methods

The primary analysis will be conducted under an ITT framework. Descriptive statistics will be produced as outlined in Section 4.1.

The purpose of the primary objective is to assess the impact of the CTH intervention on the rate of opioid OD deaths during the evaluation period in the HCS communities (i.e., deaths with an underlying cause of drug poisoning) where opioids were determined to be contributing (alone or in combination with other drugs) to the drug poisoning. To address this objective, the statistical model outlined below will evaluate the primary hypothesis (see Section 2.3.1) by testing the difference in the rate of opioid OD deaths during the evaluation period between Wave 1 and Wave 2 communities.

1. **Outcome Variable:** Number of opioid OD deaths during the evaluation period as defined in Section 6.1.
2. **Statistical Model:** Negative binomial.
3. **Offset:** The natural log of the community population size during the most recent year from available data.
4. **Covariates:** The natural log of the baseline rate of opioid OD deaths, rural/urban status, and RS (KY, MA, NY, OH). If there are any communities where the baseline rate of opioid OD deaths is 0, the log transformation cannot be applied and so the baseline rate of opioid OD deaths will be used across all models of this outcome.

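### As written, the post hoc baseline-versus-evaluation model in SAP 6.4 gives both periods the same population offset, so its within-wave relative rates estimate ratios of expected counts

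*SAP*

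**What the plan says.** SAP 6.4 describes a marginal model, added after Version 3.0 had been implemented and its results disseminated, that "was fit to the number of opioid overdose deaths during the baseline and evaluation periods". Each community therefore supplies two records. Baseline is the "12 months from January 2019 to December 2019 immediately preceding the study initiation" (SAP 5.5). Evaluation is the "12-month period from July 1, 2021 to June 30, 2022" (SAP 2.1).

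Wave, site and rurality enter as main effects. Change over time is carried by "time period (baseline or evaluation period), and a two-way interaction between wave and time period". Population enters only once, through this clause: "as well as an offset term given by the natural log of the community population size during the most recent year from available data". No other offset is given, and no 2019 population is mentioned.

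The first reported quantity is "The adjusted relative rate (and 95% CI) of opioid overdose deaths between the evaluation and baseline periods in Wave 1 communities". The second is its Wave 2 counterpart. The intervention effect is the ratio of the two.

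The offset wording repeats that of the primary model in SAP 6.2.1: "The natural log of the community population size during the most recent year from available data". The primary model has a single record per community, for the evaluation period. Protocol Appendix A (12.1.1, population size adjustment) specifies the July 1 estimate for the calendar year in which the deaths are counted.

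**The concern.** In the primary model, a recent-year population is a sensible denominator because only evaluation-period deaths are modelled. In a two-period model, the same phrase assigns a later population to the 2019 deaths. Any population change between 2019 and the evaluation period is then absorbed into what is reported as a change in the death rate.

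At stake is the meaning of two estimates reported with 95% confidence intervals. They would carry the label of rate changes while making no allowance for population change. If growth differed between the waves, their ratio, which is this model's intervention effect, would carry the difference as well.

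**Working it through.** The documents give no numerical result for this model, so there is no stated figure to reproduce. The check is algebra plus a numerical confirmation.

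**Algebra.** For community i in period t (0 = baseline, 1 = evaluation), the expected count is

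μ_it = n_it × exp(x_i'β + τt + δ·wave_i·t),

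where n_it is the population in the offset and x_i holds the terms that do not change over time (wave, site, urban/rural).

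1. *Common offset* (n_i0 = n_i1): μ_i1/μ_i0 = exp(τ + δ·wave_i). The population drops out, so the within-wave quantity is a ratio of expected counts, whichever year supplied n.
2. *Period-specific offsets*: exp(τ + δ·wave_i) = (μ_i1/μ_i0)/g, with g = evaluation-period population / 2019 population. This is the rate ratio.
3. The common-offset estimate therefore equals the rate ratio times g. It is too high where the population grew and too low where it shrank.
4. The intervention effect under a common offset equals the period-specific one times g1/g2 (Wave 1 growth over Wave 2 growth). If g1 = g2, the factor is 1.

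**Numerical check.** From the SAP: 34 Wave 1 and 33 Wave 2 communities (3.1), k = 0.0431, and death probabilities between 0.000255 and 0.000436 (3.3). Assumed, because the documents give none of them: community sizes, true evaluation/baseline rate ratios of 1.2 (Wave 1) and 1.3 (Wave 2), and g. One data set was simulated per scenario and fitted both ways with a marginal model (independence working correlation). Only comparisons within a row are meaningful, since differences between rows include simulation noise.

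Poisson fit, common offset → period-specific offset:

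| Assumed g1 / g2 | Wave 1 ratio | Wave 2 ratio | Intervention effect |
|---|---|---|---|
| 1.02 / 1.02 | 1.2103 → 1.1866 | 1.2939 → 1.2685 | 0.9354 → 0.9354 |
| 0.98 / 0.98 | 1.1462 → 1.1696 | 1.2944 → 1.3208 | 0.8855 → 0.8855 |
| 1.01 / 0.99 | 1.2662 → 1.2537 | 1.2783 → 1.2912 | 0.9906 → 0.9709 |
| 1.02 / 0.98 | 1.2124 → 1.1887 | 1.2343 → 1.2595 | 0.9823 → 0.9438 |

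In the first row, 1.2103/1.02 = 1.1866 and 1.2939/1.02 = 1.2685, as the algebra requires. In the last two rows the common-offset intervention effect is higher by 1.01/0.99 = 1.0202 and 1.02/0.98 = 1.0408, that is, about 2.0% and 4.1%.

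Under the Poisson fit, the common-offset within-wave ratios equalled the raw ratios of death totals to four decimals. Under the negative binomial fit they did not: in the first scenario Wave 1 gave 1.2618 against a raw 1.2103, because communities are weighted differently. The common/period-specific ratio was still exactly g (1.2618/1.2370 = 1.02).

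**The case against.** The strongest reply is that the SAP does not clearly prescribe a common offset. The phrase about the most recent year carries no period index. SAP 6.2.1 uses the same phrase for the primary model and then describes that offset as the evaluation-period population, meaning the population for the period of the deaths. SAP 6.4 calls its model similar to those in 6.2.6, where the offset is made specific to each record. Read together with Protocol Appendix A, analysts could well have used a 2019 population for the 2019 records.

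That is possible, and the documents do not show how the model was run. But 6.2.6 makes the offset specific to levels of sex, race/ethnicity and age and never mentions time period, while 6.4 states its own offset explicitly. The rule as written yields the wrong quantity. If it was not followed, the SAP misdescribes the analysis.

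The second reply is that the model's target, the ratio of the two within-wave ratios, is largely protected. This stands. Common growth cancels exactly. Communities were randomized within research site, with constraints on population size, death rate and rural/urban status (SAP 3.2), so there is no reason to expect systematically different growth. Population change was not itself constrained, so equality is not guaranteed, but no document figure shows a difference.

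The third reply is that period-specific offsets recover the rate ratio only if the two populations come from a comparable series. A break between series would enter the result as apparent population change. This also stands, and it shapes the fix.

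**Conclusion.** The point holds for the text of SAP 6.4. With the offset as stated, the within-wave results estimate ratios of expected counts and differ from rate ratios by the population change from 2019 to the evaluation period. This departs from the denominator rule in Protocol Appendix A.

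The size rests wholly on assumption. The period midpoints are 2.5 years apart (mid-2019 to the start of 2022), so a total change of -2% to +2% corresponds to roughly 0.8% a year (2/2.5). Over that range each within-wave ratio is off by up to about 2%, and the intervention effect does not move if growth is equal. The 4.1% shift in the table needs one wave growing 2% while the other shrinks 2%, which nothing in the documents suggests.

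A reader might infer three stronger things that the documents do not support:

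- That the disseminated results were computed with a common offset. The SAP gives a rule but does not establish how the model was run.
- That the within-wave figures are simply crude ratios of death totals. That is exact for the Poisson fit but not for the negative binomial.
- That the intervention effect is biased. It is affected only by differential growth.

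The analysis is post hoc, and the primary model, with one record per community, is unaffected. This is a minor correction worth making.

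**What to change.** State the offset by record in SAP 6.4: log of the 2019 population for the baseline record and log of the evaluation-period population for the evaluation record, both from one consistent series. Because the evaluation period spans two calendar years, name the estimate used for it. Then re-run the model.

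If period-specific populations were already used, only the SAP sentence needs correcting. If a common offset is deliberately kept, label the within-wave results as ratios of counts and say that the intervention effect assumes equal population growth in the two waves.

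The cost is one re-run plus confirming that 2019 populations are available from a consistent source. SAP 5.5 calls for 2019 baseline rates, so some denominator exists, but its year is not stated. SAP 3.2 also shows that the population figures used at randomization were defined differently for Massachusetts.

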6.5 Harms

In the HCS main trial, emergency medical service (EMS) runs for suspected opioid-related OD, as defined by each research site, were monitored as a safety measure. The four HCS RSs already had access to EMS runs that could be requested at monthly frequency, with a 15-day lag after the end of each month. The HCS estimated the rate of suspected opioid-related OD deaths by month in a community as number of events per 1,000 community residents. In this manner, EMS runs provided the HCS main trial DSMB team with an early warning sign of an increase in the rate of opioid overdose deaths in HCS communities. A three-month moving average of the rate of opioid OD deaths was calculated using the EMS data. If a single month had an estimated rate that was more than three standard deviations above this moving average, then an adverse event (AE) was considered to have occurred. If a single month had an estimated rate that was more than four standard deviations above this moving average, then a serious adverse event (SAE) was considered to have occurred. The HCS also follows a metric-based approach to identify safety signals. If any of the following metrics are observed, a detailed review of the events will be conducted to evaluate their relatedness to the HCS. Monthly metrics are triggers observed in a single month across all communities: a) five AEs, b) two SAEs, or c) one SAE + three AEs. Cross-month metrics are triggers observed across all months in a single community: a) three consecutive AEs, b) consecutive AE and SAE. For final analysis, AE and SAE events and rates per 1,000 will be summarized by wave, RS, and wave by RS. Also, the actual number of opioid-related EMS OD runs and rates per 1,000 will be summarized by wave, RS, and wave by RS.

6.6 Statistical Software

The SAS statistical package (version 9.4 or higher) will be utilized for all analyses. The R software package may be used to create figures and other graphical displays.

6.7 List of Potential Displays

Listing of proposed table shells and figures for specified analysis.

- Figure 1: CONSORT Diagram
- Table 1. Baseline Demographic Characteristics of N=67 Communities Participating in the HEALing Communities Study by Wave (January 2019 – December 2019)
- Table 2a. Descriptive Means of the Rate of Opioid Overdose Deaths During the Evaluation Period in the Intention-to-Treat Population
- Table 2b. Descriptive Means of the Rate of Opioid Overdose Deaths During the Evaluation Period in the Per Protocol Population

- Table 3a. Descriptive Sums of the Rate of Opioid Overdose Deaths During the Evaluation Period in the Intention-to-Treat Population
- Table 3b. Descriptive Sums of the Rate of Opioid Overdose Deaths During the Evaluation Period in the Per Protocol Population
- Table 4. Effect of the CTH Intervention on the Rate of Opioid Overdose Deaths During the Evaluation Period
- Table 5. Modification of the Effect of the CTH Intervention on the Rate of Opioid Overdose Deaths During the Evaluation Period by Strata (RS, Rural/Urban Status, Sex, Race/Ethnicity, Age) in the Intention-to-Treat Population
- Table 6a. Actively Implemented Strategies from ORCCAT Menu 1: Overdose Education and Naloxone Distribution by Study Site for N=33 Wave 1 Communities Participating in the HEALing Communities Study
- Table 6b. Actively Implemented Strategies from ORCCAT Menu 2: Medication for Opioid Use Disorder by Study Site for N=33 Wave 1 Communities Participating in the HEALing Communities Study
- Table 6c. Implemented Strategies from ORCCAT Menu 3: Safer Prescribing by Study Site for N=33 Wave 1 Communities Participating in the HEALing Communities Study
- Table 7. Safety Outcomes by Wave and Research Site in the Intention-to-Treat Population
- Table 8. Protocol Deviations by Research Site in the Intention-to-Treat Population by Wave
- Other figures and tables that may be needed for didactic purposes.

8 APPENDICES

8.1 Appendix 1: Study Randomization

Table A1.1: HCS Wave 1 Communities

Wave	RS	CID	Community Name	Rural/Urban
1	KY	02	BOYD	Urban
1	KY	03	BOYLE	Rural
1	KY	06	CLARK	Urban
1	KY	07	FAYETTE	Urban
1	KY	08	FLOYD	Rural
1	KY	09	FRANKLIN	Rural
1	KY	13	KENTON	Urban
1	KY	15	MADISON	Rural
1	MA	18	BROCKTON	Urban
1	MA	19	PLYMOUTH	Urban
1	MA	20	GLOUCESTER	Urban
1	MA	22	SALEM	Urban
1	MA	23	HOLYOKE	Urban
1	MA	25	LOWELL	Urban
1	MA	28	BARNSTABLE (BOURNE/SANDWICH)	Rural
1	MA	32	MIDDLESEX (SHIRLEY/TOWNSEND)	Rural
1	NY	34	CAYUGA	Rural
1	NY	36	COLUMBIA	Rural

HCS Protocol (MP0048)

Statistical Analysis Plan for the HCS Main Trial Results

Wave	RS	CID	Community Name	Rural/Urban
1	NY	38	ERIE	Urban
1	NY	40	GREENE	Rural
1	NY	41	LEWIS	Rural
1	NY	44	PUTNAM	Urban
1	NY	45	SUFFOLK	Urban
1	NY	47	ULSTER	Urban
1	OH	50	ASHTABULA	Rural
1	OH	51	ATHENS	Rural
1	OH	53	CUYAHOGA	Urban
1	OH	54	DARKE	Rural
1	OH	56	GREENE	Urban
1	OH	57	GUERNSEY	Rural
1	OH	58	HAMILTON	Urban
1	OH	61	LUCAS	Urban
1	OH	62	MORROW	Urban
1	OH	64	SCIOTO	Rural

Table A1.2: HCS Wave 2 Communities

Wave	RS	CID	Community Name	Rural/Urban
2	KY	01	BOURBON	Urban
2	KY	04	CAMPBELL	Urban
2	KY	05	CARTER	Rural
2	KY	10	GREENUP	Urban
2	KY	11	JEFFERSON	Urban
2	KY	12	JESSAMINE	Urban
2	KY	14	KNOX	Rural
2	KY	16	MASON	Rural
2	MA	17	NORTH ADAMS	Urban
2	MA	21	LAWRENCE	Urban
2	MA	24	SPRINGFIELD	Urban
2	MA	26	PITTSFIELD	Urban
2	MA	27	WEYMOUTH	Urban
2	MA	29	BRISTOL (BERKELEY/DIGHTON/FREETOWN)	Rural
2	MA	30	FRANKLIN (GREENFIELD/MONTAGUE/ATHOL/ORANGE)	Rural
2	MA	31	HAMPSHIRE (BELCHERTOWN/WARE)	Rural
2	NY	33	BROOME	Urban
2	NY	35	CHAUTAUQUA	Rural
2	NY	37	CORTLAND	Rural
2	NY	39	GENESEE	Rural
2	NY	42	MONROE	Urban
2	NY	43	ORANGE	Urban
2	NY	46	SULLIVAN	Rural
2	NY	48	YATES	Urban
2	OH	49	ALLEN	Urban
2	OH	52	BROWN	Urban
2	OH	55	FRANKLIN	Urban
2	OH	59	HURON	Rural
2	OH	60	JEFFERSON	Urban
2	OH	63	ROSS	Rural
2	OH	65	STARK	Urban
2	OH	66	WILLIAMS	Rural
2	OH	67	WYANDOT	Rural

8.2 Appendix 2: Additional RS-specific inclusion criteria for communities enrolled in the HCS

Criteria	Kentucky	Massachusetts	New York	Ohio
Number of communities	16 counties	16 cities/towns	16 counties	19 counties
Additional criteria	Selected counties that had (1) a syringe service program (marker of community readiness), (2) a jail, (3) ≥ 1 buprenorphine-waivered provider, and (4) ≥ 5 opioid overdose deaths in 2017	Selected to minimize proximity and contamination, favored communities with an anchor office-based addiction treatment program and a pre-existing substance use coalition	Selected the communities of Buffalo in Erie County, Rochester in Monroe County, and the Brookhaven township in Suffolk County to keep size comparable	Randomly selected counties stratified by urban/rural that (1) were not contiguous and (2) did not share an alcohol, drug and mental health board

8.3 Appendix 3: SAS Code Examples

Exhibit 8.3.1: An example of SAS PROC GLIMMIX code to be used for the primary analysis of the primary hypothesis.

```
PROC GLIMMIX DATA=ALLCOMM empirical = FIRORES (or ROOT) MAXLMMUPDATE=100 ;  
TITLE1 "NEGATIVE BINOMIAL MODEL BASED ON GLIMMIX";  
MODEL NOPDEATHS = OPDEATH_BL SITE2 SITE3 SITE4 RURAL GRP_CODE /  
OFFSET=LOGCOMM_POP ddfm = none ddf = 60, 60, 60, 60, 60, 60, 60, 60 DIST=NEGBIN S;
```

where:

NOPDEATHS = primary outcome, the number of opioid OD deaths during the evaluation period for each community

OPDEATH_BL = baseline rate of opioid OD deaths for each community

SITE2, SITE3, SITE4 = indicator variables for RS, referencing comparison to SITE = 1 (insert RS that = 1)

RURAL = rural/urban status for each community (1 = rural, 0 = urban)

GRP_CODE = intervention arm (1 = CTH intervention, 0 = wait-list control)

LOGCOMM_POP = natural log of community population size during the evaluation period, which is implicitly in the equation accounting for variation in population size, and hence the variation in denominators for rates among communities

DIST = NEGBIN signifies a negative binomial error structure; essentially allowing the underlying Poisson rate of opioid OD deaths during the evaluation period to vary across communities
